2.2.2 Baseline and change from baseline

Two baselines are defined:

- Baseline is the last available value prior to first administration of efgartigimod in the first cycle in 1705.
- CnB: Cycle n Baseline i.e. last available value prior to first administration of efgartigimod in cycle n, with n=1, 2, 3, etc..

Note: for MG-ADL and QMG, all assessments on the day of first administration of the IMP in cycle n are considered in the baseline selection, also those post-administration.

Change can be calculated from baseline or CnB. Note: baseline coincides with C1B. Baseline will be considered for analyses that assess across all cycles and the CnB will be used for analyses restricted to a specific cycle, n.

Change for safety parameters will be calculated from baseline only.

For efficacy and PD, a (percent) change can be calculated from baseline or CnB, according to the analysis.

	Statistical Analysis Plan	
ARGX-113-1705	Final Analysis	Final 1.0 of 20SEP2022

Change from baseline at time point t = value at time point t – baseline value.

Percent change from baseline at time point t = (actual value at time point t -baseline value)*100/baseline value.

Change from CnB at time point t = value at time point t – CnB value.

Percent change from CnB at time point t = (actual value at time point t - CnB value)*100/CnB value.

2.2.3 *Relative day*

Relative days in the period (ADYP) will be calculated according to the following rule:

- Concerned date < reference date: ADYP = concerned date – reference date
- Concerned date ≥ reference date: ADYP = concerned date – reference date + 1

The reference date is the date of first administration of study drug in the specific period, except for assessments in ITP0, for which the date of informed consent in 1705 will be taken as reference date.

2.2.4 *Analysis visits*

All assessments (from first ARGX-113-1705 cycle on), including unscheduled assessments, will be allocated to analysis windows. Tables and listings will present the analysis windows as defined below, not the CRF visits. Allocation of assessments will be done using their relative day in the period (see section 2.2.3).

Table 4: Analysis visits

Phase/Period	Analysis window	Target ADYP	Lower limit ADYP	Upper limit ADYP
Treatment/ cycle n (=Treatment Period n + ITP_n)				
	CnB	1	-INF	1*
	Week 1	8	1*	11
	Week 2	15	12	18
	Week 3	22	19	35
	Week 7	50	36	63
	Week 7 + (4*x)	50 + (x*28)	50 + (x*28) - 14	50 + (x*28) + 13

* An assessment on day 1 will be attributed to CnB in case it is before the infusion, to week 1 otherwise, except for MG-ADL and QMG (see section 2.2.2)

Baseline is defined in section 2.2.2.

For those patients who will start a new cycle, the last assessment in a cycle, prior to the infusion of the new cycle, will be allocated to the appropriate visit within the previous cycle and will also be allocated as the CB visit of the new cycle.

Per parameter and analysis window, the value closest to the target ADYP will be used in analysis tables and figures, other values will only be listed. If more than one value is located at the same distance from the target, then the latest in time will be selected.

	
Statistical Analysis Plan
	

ARGX-113-1705
	
Final Analysis
	
Final 1.0 of 20SEP2022

The value latest in time will be identified using, in order of preference, the assessment time, the visit label or the group identifier. Missing values are removed before the selection is made.

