If a patient becomes eligible for (re-)treatment with efgartigimod by meeting the criteria for the total MG-ADL score as stated in [Section 4.1](#), but cannot complete the entire treatment period during Part A (ie, after day 336) then the patient can be transitioned to Part B after completing the end of Part A (EoA) visit assessments ([Table 1](#)). These assessments should be completed even if the patient is unwilling or unable to continue to Part B.

The transition to Part B can be either at ITPE₀V_n or TPE₁V₁, depending on the patient status regarding the need for (re-)treatment upon transition from Part A. The first visit in Part B will always coincide with the EoA visit in Part A. The assessments done for the last visit in Part A should not be repeated in Part B.

(RE-)TREATMENT (Part B)

If the patient feels that his/her condition has deteriorated, then the investigator may start a new treatment period at an intertreatment period (ITPE) visit or the patient may contact the investigator to attend an unscheduled visit.

A patient can start the next treatment period and receive efgartigimod if all of the following criteria are met:

- The patient has completed the previous treatment period (ie, after visit 4)*
- The investigator determines that the patient will benefit from re-treatment
- There is at least 1 calendar month (minimum 4 weeks) between treatment periods (ie, between TPE_nV4 and TPE_{n+1}V1)

*A patient who has had a temporary interruption of trial treatment in Part A may also continue into Part B of the trial and receive (re-)treatment if the conditions in Section 4.4.1 are met.

However, patients may not receive (re-)treatment with efgartigimod if, at the time of (re-)treatment, they have clinical evidence of bacterial, viral or fungal disease, or any other significant disease which could confound the results of the trial or put patients at undue risk.

If a patient becomes eligible for (re-)treatment with efgartigimod but cannot complete the entire treatment period within the duration of the trial, the patient should continue to the EoS visit.

If the investigator considers that the patient will not have a clinical benefit from (re-)treatment then the patient cannot start a new treatment period. The patient should then continue to the EoS visit.

STANDARD OF CARE (SoC)

In Part A:

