Permitted SoC for MG treatment under this protocol include NSIDs (eg, azathioprine, methotrexate, cyclosporine, tacrolimus, mycophenolate mofetil, and cyclophosphamide), steroids, as well as acetylcholinesterase (AChE) inhibitors.

A change of the type or dose/regimen of SoC (replacing, adding or removing SoC, or adjustment of the SoC dose and/or frequency) is not allowed:

- From trial entry until 1 week after the last infusion of the first treatment period.
- From the first infusion until 1 week after the last infusion of each subsequent treatment period.

From 1 week after the last infusion of each treatment period up to and prior to the administration of the first infusion of the next treatment period, a dose reduction in SoC consistent with current medical practice is allowed.

In case these medications are taken for another indication than MG, same conditions apply.

Administration of AChE inhibitors must be halted for at least 12 hours prior to performing the QMG assessment. Following this requirement, this possible temporary change in dosing regimen of AChE inhibitors will not be considered as a change in SoC.

In Part B:

A change of the type or dose/regimen of SoC (replacing, adding or removing SoC, or adjustment of the SoC dose and/or frequency) is allowed, without restrictions, following current medical practice.

PLEX, intravenous immunoglobulin (IVIg), immunoadsorption or use of a new type of corticosteroid or an increased dose of the current corticosteroids used as stand-alone therapy or in combination is also allowed in Part B.

TIME BETWEEN TREATMENT PERIODS

At the end of each treatment period, patients will enter a variable intertreatment period during which they will be treated with their SoC only. The length of the intertreatment period may vary from patient to patient and for each patient from period to period (patient-tailored approach). For Part A, the visit frequency in the Intertreatment period is every 30 days (± 2 days) after the previous visit. For Part B, the visit frequency in the intertreatment period is every 90 days (± 7 days) after the previous visit. If an ITP visit for Part A is scheduled within 14 days of the EoA visit, then the EoA visit should be performed instead.

RESCUE THERAPY (Part A only)

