5.3. Intertreatment Period

Intertreatment period visits occur every 30 days after the previous visit in Part A and every 90 days after the previous visit in Part B.

At each ITP_nV_n (Part A) or ITPE_nV_n (Part B) an evaluation of the need for (re-)treatment should be done. In case the patient is not in need of (re-)treatment, assessments for ITP_nV_n (Part A) or ITPE_nV_n (Part B) should be performed as listed below and per the General Schedule of Assessments for Part A (Table 1) or for Part B (Table 2). However, in case the evaluation shows that the patient is in need of (re-)treatment and is also eligible for (re-)treatment, the assessments according to TP_nV1 (Part A) or TPE_nV1 (Part B) are to be performed instead (see Section 5.2). If an ITP visit for Part A is scheduled within 14 days of the EoA visit, then the EoA visit should be performed instead.

The following assessments will be performed in Part A:

- Assessments of disease severity – the MG-ADL scale should be administered before the QMG scale
- Suicidality assessment
- Physical examination
- Weight will only be measured in case there is an obvious weight change compared to the last weight assessment
- Vital signs
- ECG
- Clinical laboratory tests. Patients need to be fasted at least 8 hours prior to sampling
- Urinalysis

- Urine pregnancy test (only for women of childbearing potential, see [DEFINITION OF TERMS](#))
- Pharmacodynamic biomarkers (anti-AChR antibodies in AChR-Ab seropositive patients only, total IgG and subtypes [IgG1, IgG2, IgG3 and IgG4], and anti-MuSK antibodies in MuSK-Ab seropositive patients only)
- Review of concomitant medication and rescue therapy
- Assess AEs, if any

The following assessments will be performed in Part B:

- Assessments of disease severity (MG-ADL scale)
- Vital signs
- ECG
- Urine pregnancy test (only for women of childbearing potential, see [DEFINITION OF TERMS](#))
- Review of concomitant medication
- Assess AEs, if any

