8. STATISTICS

The statistical analyses will be performed by sponsor's designated CRO using statistical analysis systems SAS® (SAS Institute, Cary, NC, United States [US]) version 9.2 or higher, and the software package R, if applicable. The standard operating procedures (SOPs) and work instructions of sponsor's designated CRO will be used as the default methodology if not otherwise specified.

Any change to the data analysis methods described underneath will be mentioned in the statistical analysis plan (SAP). Any additional analysis, and the justification for making the change, will be described in the Clinical Trial Report (CTR). Additional exploratory analyses of the data will be conducted as deemed appropriate.

Due to the single-arm, open-label nature of the design, evaluation of all endpoints will be essentially descriptive. Endpoints will be summarized by treatment (as received in ARGX-113-1704).

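### By-cycle MG-ADL rows after Week 3 pool routinely seen Part A patients with Part B patients seen mainly because they need re-treatment, so Week 7 is expected to lean toward worse scores

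*SAP*

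**What the plan says.** **Visit schedule.** Protocol 5.3: "Intertreatment period visits occur every 30 days after the previous visit in Part A and every 90 days after the previous visit in Part B". The windows are ±2 and ±7 days. The fourth infusion visit (V4) is at X+21 ±1 in both parts.

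**Part B re-treatment.** Protocol 4.1 sets no MG-ADL threshold. It relies on the investigator's judgement and a minimum gap: "There is at least 1 calendar month (minimum 4 weeks) between treatment periods". The prompt is the patient's own sense of worsening: "If the patient feels that his/her condition has deteriorated, then the investigator may start a new treatment period at an intertreatment period (ITPE) visit", or at an unscheduled visit.

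**Windowing.** Under SAP 2.2.4 all assessments, "including unscheduled assessments, will be allocated to analysis windows". For a patient starting another cycle, the last assessment before the new infusion "will be allocated to the appropriate visit within the previous cycle" and is used a second time as the baseline of the new cycle.

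**Pooling.** SAP 2.4.3 allocates Part B data to cycles in the same way as Part A data, without separate tables. SAP 2.3.1 imputes nothing. SAP 4.1.1 analyses MG-ADL in both parts, although Protocol 3.3 lists MG-ADL change as a Part A-only tertiary endpoint. SAP 8.1 has MG-ADL tables without telephone visits, but none by part.

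**The concern.** In Part A the double use of the pre-dose value is sound. Everyone still in the cycle is due at about day 52. If re-treatment is needed then, the new cycle's first-visit assessments replace the routine ones (Protocol 5.3), and mapping that value back completes the Week 7 sample.

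Part B has no routine visit for the rule to complete. A patient who stays well has no Week 7 value, while a patient re-treated at that time has one. Presence in the row then depends on the outcome being summarised, and an observed-case mean does not correct for this.

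Later cycles hold more Part B data, so the mix changes with cycle number. On the maximum of six Part A treatment periods used for the blood-volume estimate in Protocol 7.2.2, cycles beyond the sixth would hold no Part A data. A reader comparing Week 7 across cycles could take a change in who is observed for a change in response.

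**Working it through.** **1. The plan's own windows.** SAP 2.2.4 gives the later windows as 50 + 28x − 14 to 50 + 28x + 13. At x = 0 this is 36 to 63, which matches the stated Week 7 row. The next ones are Week 11 = 64–91, Week 15 = 92–119, Week 19 = 120–147, Week 23 = 148–175, Week 27 = 176–203, Week 31 = 204–231 and Week 35 = 232–259.

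**2. Routine visits on the cycle-day scale.** With first infusion on day 1, V4 is day 22 (21 to 23).

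| Visit | Nominal day | Range | Window |
|---|---|---|---|
| Part A, 1st intertreatment | 22 + 30 = 52 | 21 + 28 to 23 + 32 = 49–55 | Week 7 |
| Part A, 2nd | 82 | 77–87 | Week 11 |
| Part A, 3rd | 112 | 105–119 | Week 15 |
| Part B, 1st intertreatment | 22 + 90 = 112 | 21 + 83 to 23 + 97 = 104–120 | Week 15 (day 120: Week 19) |
| Part B, 2nd | 202 | 187–217 | Week 27 or 31 |
| Part B, 3rd | 292 | 270–314 | Week 39 or 43 |

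No routine Part B intertreatment visit falls in Weeks 7, 11, 23 or 35, and only day 120 reaches Week 19.

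**3. What can fill the gaps in Part B.**
- Pre-dose value of the next cycle: earliest at 22 + 28 = day 50 (49 to 51), the Week 7 target day.
- Unscheduled visits: any day.
- ED visit 30 ± 2 days after V4: days 49–55, in Week 7.
- ED visit before transfer to ARGX-113-2002, with the last IV dose at least 30 days before entry: Week 7, Week 11 or later.
- EoS at day 1095 or on drug availability: any cycle day.

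**4. Direction and size (illustrations; every input is assumed).** With n_A Part A and n_B Part B patients in a cycle, and a fraction p of Part B patients having a value in the window:

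pooled mean = (n_A·m_A + p·n_B·m_B) / (n_A + p·n_B)

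*Simulation.* Assumptions: best change averages about −5 points with SD 2; response is lost linearly from day 29, with a median of 30, 50 or 80 days to full loss; re-treatment follows once the change is above −2, at routine visits in Part A and within a week (not before day 50) in Part B. Part B supplies 30% or 60% of cycles.

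| Median days to full loss | Week 7, Part A | Week 7 pooled (30% / 60%) | Week 11, Part A | Week 11 pooled (30% / 60%) |
|---|---|---|---|---|
| 30 | −1.34 | −1.18 / −0.99 | −0.68 | −0.83 / −1.04 |
| 50 | −2.44 | −2.16 / −1.80 | −1.28 | −1.34 / −1.43 |
| 80 | −3.31 | −3.05 / −2.63 | −2.08 | −2.01 / −1.91 |

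Worked case (median 50, 60% Part B): p = 0.58 and m_B = −1.06, so (0.4 × −2.43 + 0.6 × 0.58 × −1.06) / (0.4 + 0.348) ≈ −1.8.

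Week 7 moves toward worse in every row, by 0.16 to 0.68 points. Week 11 moves either way, from 0.36 better to about 0.16 worse.

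*Harsher case.* Take m_A = −3, re-treated patients exactly at 0, and p = 0.3. For 40/60 Part A/Part B patients: −120 / (40 + 18) = −2.1. For 20/80: −60 / (20 + 24) = −1.4. For 10/90: −30 / (10 + 27) = −0.8. The shifts are 0.9, 1.6 and 2.2 points.

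**The case against.** **Other visits do fall in the gaps.** A reader might infer that Part B has no scheduled visit in Weeks 7 and 11, or that only re-treated patients appear there. The documents do not support that. ED visits after V4, transfer-ED visits and EoS visits can land there, and transfer and EoS visits are not prompted by relapse. They occur about once per patient, in the last cycle, whereas pre-dose values recur each time another cycle starts. The relative numbers cannot be worked out, because neither document gives Part B counts or re-treatment timing.

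**A worse picture in every late row is not shown.** Part A patients re-treated at Week 7 have already left the cycle by Week 11, and Part B patients may be re-treated before their scores fall as far. This stands, and it limits the directional claim to Week 7.

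**The harsher illustration is extreme.** It places every re-treated patient exactly at baseline, although Part B has no score threshold. It also holds p at 30% in late cycles, which frequently re-treated patients are more likely to reach. This stands.

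**Most of the response picture is untouched.** MG-ADL has the same schedule through Week 3 in both parts. Maximum drop and minimum score per cycle (SAP 4.1.2) are not worsened by a relapsed pre-dose value, and cycle-duration tables show re-treatment timing directly. The trial is descriptive (Protocol 8: "evaluation of all endpoints will be essentially descriptive"). This stands, so a reader should not infer that the by-cycle tables as a whole would show fading response.

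**Conclusion.** The point holds for the by-cycle MG-ADL rows after Week 3. Following the plan as written makes Part B presence at Weeks 7, 11 and 23, and nearly all of Week 19, depend largely on re-treatment or an unscheduled visit. Pooled Week 7 MG-ADL is expected to lean toward worse values, and more so as the Part B share grows. This assumes that re-treated Part B patients score worse on average than those who stay away, which fits the protocol's deterioration prompt. Week 11 is selectively sampled with uncertain direction. The documents give no basis for a size; the figures above show only how it varies with the assumptions.

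Vital signs and ECG by-visit rows share the sampling gap. Because these are components of the primary endpoint, a reader might infer a biased safety result. Nothing in the documents links MG relapse to a direction of change in blood pressure or QTc, and worst-case tables use all post-baseline values whatever the window (SAP 2.2.5). QMG and pharmacodynamics are Part A only, and Part B laboratory results are not in the database. This is a presentation fault in a tertiary endpoint that is cheap to correct; it does not threaten the trial's main conclusions.

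**What to change.** In SAP 2.2.4 and 2.4.3:

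1. Flag assessments made on the Part B schedule, meaning on or after the end-of-Part-A visit, including those in cycles that straddle it.
2. For MG-ADL, present post-Week 3 by-visit rows for Part A-schedule data only, or place a Part A-restricted companion table beside the pooled one. This matches the protocol's Part A-only endpoint and follows the SAP's own practice of repeating tables without telephone visits.
3. State that the restricted rows exclude Part B unscheduled and next-cycle pre-dose values in windows with no routine Part B visit (Weeks 7, 11, 19, 23 and later gaps such as Week 35), and say how ED and EoS values are handled.
4. Keep all values in listings, cycle baselines, minimum score, maximum drop and worst-case.
5. Leave the vital signs and ECG by-visit tables intact, with a footnote on the sparser Part B visits.

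Cost: a few SAP sentences, a flag in the analysis dataset, and either one extra table or fewer observations in late-cycle rows. Some of those rows may fall below the 10-subject display rule in SAP 2.4.1.

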2.2.5 Worst-case

A worst-case analysis visit will be created for parameters for which abnormalities and/or toxicity grades are defined to summarize values considered as the worst-case. For abnormalities it is derived per parameter and in case both the lowest and the highest values are considered abnormal, a patient can have two worst-case analysis visits for a same parameter. For toxicity grades the worst-case is the value associated to the highest toxicity grade and is derived per parameter and toxicity direction (hypo / hyper).

All non-missing post-baseline values, including unscheduled assessments will be considered when deriving the worst-case analysis visit.

2.3 IMPUTATION AND ROUNDING RULES

2.3.1 Missing values

No imputation will be done of missing values (i.e. observed cases analysis).

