4. INVESTIGATIONAL PLAN

4.1. Summary of Trial Design

Methodology

DESCRIPTION

This is a 3-year (maximum), single-arm, open-label, multicenter, phase 3 follow-on trial of ARGX-113-1704 to evaluate the long-term safety and tolerability of efgartigimod in patients with gMG. The trial consists of 2 parts: Part A (1 year) and Part B (up to maximum 2 years or until efgartigimod becomes commercially available or another option to access efgartigimod is available, whichever option comes first. The additional part (Part B) was added to ARGX-113-1705 in order to provide the patients with the chance to have access to efgartigimod while it is not yet commercially available or available through another patient program. This extension will also enable additional long-term safety and tolerability data to be collected.

A variable number of treatment periods consisting of 4 weekly infusions of efgartigimod (10 mg/kg of body weight) infused over a period of 3 weeks will be administered to eligible patients on an “as needed basis” on top of their SoC. The time between treatment periods is based on the duration of the treatment effect and may vary from patient to patient and within each patient from period to period (patient-tailored approach).

The first visit of trial ARGX-113-1705 will coincide with the last visit of trial ARGX-113-1704 for each patient.

The SEB will be set at the first trial visit, while the baseline of each subsequent treatment period (TP_nB for Part A or TPE_nB for Part B) will be set at visit 1 of each corresponding treatment period.

ROLL-OVER

At the EoS visit of trial ARGX-113-1704, eligible patients will be offered the option to roll over into this trial. Patients in need of (re-)treatment in trial ARGX-113-1704 but who cannot complete a Treatment Cycle within the time frame of that trial, may immediately roll over to this trial to receive treatment with efgartigimod.

Patients who discontinued early from trial ARGX-113-1704 or discontinued early from randomized treatment for rescue or pregnancy reasons or for an SAE that is likely to result in a life-threatening situation or pose a serious safety risk in that trial will not be offered the option to roll over into this trial.

Patients who discontinued early from randomized treatment for other reasons and patients who had a temporary interruption from randomized treatment in trial ARGX-113-1704 may be offered the option to roll over into this trial.

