Patients who have completed at least 1 cycle of treatment and at least 1 year of trial ARGX-113-1705 and have started Part B are eligible to enroll in the open-label trial ARGX-113-2002 to receive efgartigimod by SC administration.

Before enrolling in ARGX-113-2002 from Part B, patients must first complete the early discontinuation (ED) visit assessments specified in [Table 2](#). The previous efgartigimod IV dose must have been received at least 30 days before entry into ARGX-113-2002.

Patients can enroll in ARGX-113-2002 until recruitment for this study is closed. Patients who enroll in ARGX-113-2002 will not return to ARGX-113-1705.

(RE-)TREATMENT (Part A)

Each patient will start a (new) treatment period with efgartigimod when all of the following criteria are met:

- The patient has completed the previous treatment period (ie, after visit 4)
- The patient has a total MG-ADL score of ≥ 5 points with more than 50% of the total score due to non-ocular symptoms
- The patient has a reduction in the total MG-ADL score of < 2 points compared to the score at:
 1. The last treatment cycle baseline (TCB) in trial ARGX-113-1704 for the first treatment period (TP₁) in trial ARGX-113-1705
 2. The last treatment period Baseline (TP_nB) for all subsequent treatment periods (TP_{n+1}) in trial ARGX-113-1705

However, patients may not receive (re-)treatment with efgartigimod if, at the time of (re-)treatment, they have clinical evidence of bacterial, viral or fungal disease, or any other significant disease which could confound the results of the trial or put patients at undue risk. Patients who require an additional treatment but who are not eligible to receive (re-)treatment for the reasons listed here will remain in the trial to receive appropriate alternative MG treatment (see [Appendix 5](#) and [Appendix 6](#)).

Patients who have a treatment failure to efgartigimod for 3 consecutive treatment periods will be discontinued from the trial. Treatment failure means the absence of a decrease of at least 2 points in total MG-ADL score compared to the corresponding TP_nB in at least 50% of the assessments (ie, TP_nV2, TP_nV3, TP_nV4, and the first posttreatment period visit).

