2.2 PHASES, PERIODS AND TIME POINTS

2.2.1 *Phases and periods*

All events and assessments will be allocated to phases and periods (see Table 1). A patient can start in 1705 in an inter-treatment period or in a cycle, depending on the patient status regarding the need for (re-)treatment upon roll-over. Each period following ITPO coincides with a cycle and includes the 4 administrations of efgartigimod and the inter-treatment period (ITP) visits. The length of the ITP is patient specific and can differ between the different periods. The number of patients may decline for each subsequent cycle.

	Statistical Analysis Plan	
ARGX-113-1705	Final Analysis	Final 1.0 of 20SEP2022

Table 1: phase/period definition

Phase	Period	Start	End
Treatment	ITP0	Earliest of (date of signing the informed consent form (ICF) and date of roll-over), with 00:00 added as time part.	First administration date/time in cycle 1 – 1 minute
	Cycle 1	First administration date/time in cycle 1	First administration date/time in next cycle – 1 minute or if last cycle: date of last contact, with 23:59 added as time part
	Cycle n	First administration date/time in cycle n	First administration date/time in next cycle – 1 minute or if last cycle: date of last contact, with 23:59 added as time part
	Cycle x	First administration date/time in cycle x	Date of last contact, with 23:59 added as time part

AEs and concomitant medications will be allocated to phases and periods as described in sections 5.1.2 and 3.5.2 respectively. All other assessments will be allocated to phases and periods based on the assessment date/time.

In case of (partially) missing date/time fields disabling allocation or date(time) equal to dosing date(time), information from visit label and protocol schedule of assessments (SoA) will be used to allocate to the correct period. If this is not possible, assessments will be allocated to the first possible cycle (not ITP0) unless the available parts of the assessments start or stop date/time provide evidence the assessments did not occur during that period.

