4. EFFICACY, PHARMACODYNAMICS AND ANTI-DRUG ANTIBODIES ANALYSES

4.1 EFFICACY

4.1.1 *Available data*

Efficacy will be assessed using MG-ADL (part A and B) and QMG (part A only).

4.1.2 *Endpoints and derivation rules*

1) Actual values and change from baseline and CnB in total MG-ADL score will be analysed descriptively and categorically.

Categories to be used for actual values in MG-ADL total score: 0, 1, 2, 3, 4, 5-7, 8-9, 10-12, 13-16, 17-20 and 21-24.

Categories to be used for changes from baseline and CnB in MG-ADL total score: >0, 0, -1, -2, -3, -4, -5, -6, -7, -8, -9, -10, <-10. Number of patients, percentages and cumulative percentages will be shown.

In addition to the planned timepoints, following timepoints will be shown for each cycle:

- Maximum drop from baseline and CnB in MG-ADL
- Minimum MG-ADL score: descriptively and categorically

Missing data will not be considered.

Analysis will be done on AChR-Ab seropositive patients, AChR-Ab seronegative patients and overall.

2) Actual values and change from baseline and CnB in total QMG score will be described descriptively and categorically as for the MG-ADL score. For the categorization of the QMG total score actual values a category of >24 will be added.

4.1.3 *Statistical analysis*

Summary statistics will be provided in terms of absolute values and changes from baseline (overall) and CnB (for each cycle) for MG-ADL and QMG total scores in AChR-Ab seropositive patients, AChR-Ab seronegative patients and the overall safety population.

Absolute values and changes from baseline (overall) and CnB (for each cycle) in MG-ADL and QMG total scores will also be categorized, including the number of patients within each category, the percentage, and the cumulative percentage.

See section 8 for a list of tables and listings.

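### From about Week 11, by-week MG-ADL and QMG rows for Part A cycles describe only patients not yet re-treated, so benefit looks better maintained than among all who started the cycle

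*SAP*

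**What the plan says.** **Leaving a cycle.** Protocol 4.1 starts a new Part A treatment period when all its conditions hold. Two of them are "The patient has a total MG-ADL score of ≥ 5 points with more than 50% of the total score due to non-ocular symptoms" and "The patient has a reduction in the total MG-ADL score of < 2 points compared to the score at" the previous period's baseline. The same section states the principle: "The time between treatment periods is based on the duration of the treatment effect". SAP 2.2.1 (Table 1) ends a cycle at "First administration date/time in next cycle – 1 minute"; a patient's last cycle ends at last contact.

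**Placing values.** SAP 2.2.4 sets a Week 7 window (days 36 to 63) and then 28-day windows with no upper limit. The last assessment before a new infusion "will be allocated to the appropriate visit within the previous cycle" and also serves as the new cycle's baseline. Within a window, "the value closest to the target ADYP will be used in analysis tables and figures"; other values are only listed.

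**Summarising.** SAP 2.3.1: "No imputation will be done of missing values (i.e. observed cases analysis". SAP 4.1.2, for the efficacy scores: "Missing data will not be considered". Under SAP 2.4.1, by-visit percentages are taken over the patients at that visit, and a row is shown while at least 10 subjects overall contribute. SAP 2.4.3 allocates Part B data to cycles together with Part A data. MG-ADL is collected in both parts, QMG in Part A only (SAP 4.1.1).

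**Related tables.** SAP 3.1 and 8.1 plan cycle duration (Tables 14.1.1.5 and 14.1.1.6) and patients per analysis visit (Table 14.1.1.3). No time-to-re-treatment or time-to-loss-of-response analysis is planned, and the by-week tables carry no caveat.

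**The concern.** In Part A, whether a patient still contributes to a late row of a cycle is decided by MG-ADL, the variable being tabulated. A patient who has lost response and qualifies is re-treated, and every later value then belongs to the next cycle. The later rows are therefore selected by design, not by incidental missingness.

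A reader will naturally take a run of by-week rows as the time course of benefit after a cycle. The later rows instead answer a conditional question: how are the patients doing who have not yet needed re-treatment? If most early relapsers have left, the curve can flatten while the effect in all who started is fading.

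**Working it through.** The plan has no figure to reproduce: Protocol 8.1 gives no sample size, and all endpoints are descriptive (Protocol 8).

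**Step 1: where selection starts.** Window x after Week 7 has target 50 + 28x and runs from 50 + 28x - 14 to 50 + 28x + 13. This gives Week 11 = days 64-91, Week 15 = days 92-119 and Week 19 = days 120-147. Part A visits follow visit 4 (day 22) every 30 days: 22 + 30 = 52, then 82, 112 and 142, which fall in Weeks 7, 11, 15 and 19. On the scheduled visits the Week 7 value comes before any re-treatment, so selection begins at Week 11. In Part B the first scheduled visit after visit 4 is at 22 + 90 = 112, in Week 15.

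**Step 2: what happens to the loss-of-response value.** It normally enters the old cycle once, which delays the selection by one window. It can also drop out. Take a day-52 visit and an unscheduled re-treatment visit at day 60: both fall in Week 7, at 2 and 10 days from target day 50. The day-52 value is tabulated and the worsened value is only listed.

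**Step 3: size in Part A, by simulation.** One cycle, 200,000 patients, re-treated under the two MG-ADL conditions (the non-ocular condition was not modelled). None of these inputs is in the documents:
- baseline MG-ADL 9.5 (SD 2.5)
- peak drop 5 (SD 2.5)
- measurement noise SD 1.2
- lognormal time to losing half the effect, median 8, 12 or 16 weeks, log-SD 0.6 (0.3 as sensitivity)
- all, or 80%, of eligible patients re-treated at the visit

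The comparator is the same patients had nobody been re-treated. For a median of 12 weeks with all eligible patients re-treated:

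| Row | Still in cycle | Mean change, observed | Mean change, nobody re-treated | At least 2 points better, observed | At least 2 points better, nobody re-treated |
|---|---|---|---|---|---|
| Week 7 | 100% | -3.74 | -3.74 | 78% | 78% |
| Week 11 | 78% | -3.15 | -2.55 | 68% | 57% |
| Week 15 | 54% | -2.78 | -1.59 | 61% | 40% |
| Week 19 | 34% | -2.66 | -0.96 | 59% | 28% |

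Week 15 across scenarios, share at least 2 points better:

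| Scenario | Observed | Nobody re-treated |
|---|---|---|
| Median 8 weeks, all re-treated | 46% | 23% |
| Median 12 weeks, all re-treated | 61% | 40% |
| Median 16 weeks, all re-treated | 72% | 55% |
| Median 12 weeks, log-SD 0.3, all re-treated | 43% | 32% |
| Median 8 weeks, 80% re-treated | 40% | 23% |
| Median 12 weeks, 80% re-treated | 56% | 40% |
| Median 16 weeks, 80% re-treated | 68% | 54% |

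The direction is the same throughout. The gap runs from 11 points (43 - 32) to 23 points (46 - 23).

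**Step 4: choice of comparator.** Counting every re-treated patient as a failure gives lower figures, but these are just the fraction remaining times the observed share: at Week 15, 0.54 x 0.61 = 0.33, against 0.40 had nobody been re-treated. That is a different quantity, so it is not used as the measure of distortion.

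**Step 5: pooled MG-ADL tables.** It is further assumed that Part B values at Weeks 7 and 11 come from visits at which worsening patients are re-treated. Share at least 2 points better, median 12 weeks:

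| Row | Observed, 30% Part B cycles | Observed, 60% Part B cycles | All, nobody re-treated |
|---|---|---|---|
| Week 7 | 71% | 58% | 78% |
| Week 11 | 60% | 46% | 57% |
| Week 15 | 61% | 62% | 40% |
| Week 19 | 50% | 37% | 28% |

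Week 7 is too low, Week 11 changes sign with the Part B share, and Weeks 15 and 19 are too high.

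**The case against.** The case against is substantial, and several stronger readings have to be given up.

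- *The late rows show only durable responders.* A reader might infer this, but the documents do not support it. The loss-of-response value generally enters the old cycle once (SAP 2.2.4). Patients below 5 points, with mainly ocular symptoms or with an infection are not re-treated and stay in the cycle without response (Protocol 4.1). In the simulation with all eligible patients re-treated, 28% to 57% of those observed at Week 15 were not responders (100 - 72 and 100 - 43).
- *Every late MG-ADL row overstates benefit.* Also not supported. The tables pool both parts, and sparse Part B visits can reverse the direction at Weeks 7 to 11.
- *QMG is selected on itself.* It is not. Re-treatment depends on MG-ADL, so QMG is affected only through its correlation with MG-ADL, and QMG was not simulated.
- *The missing-data rule is the fault and imputation the cure.* Values after re-treatment are not missing; the cycle definition assigns them to the next cycle. Carrying forward the last value would also carry a value selected for being poor.
- *The SAP hides the attrition.* It does not. Cycle duration and patients per visit are tabulated, and each summary prints its n.
- *A duration claim is overstated.* No objective or endpoint makes one.

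The central point stands. The existing tables reveal the attrition but leave the means and percentages conditional. Cycle duration is not a substitute: a last cycle ends at last contact, so re-treatment and end of follow-up are mixed without censoring.

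**Conclusion.** The concern holds in a limited form. For cycles started in Part A, MG-ADL change and percentage improved from about Week 11 are conditional on not having been re-treated, and look better maintained than among all who started the cycle. QMG follows indirectly. In the pooled MG-ADL tables, overstatement is expected from about Week 15; before that the direction depends on the Part B share.

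Mechanism and Part A direction follow from the documents. The size does not: the Week 15 ranges (43-72% observed, 23-55% had nobody been re-treated) rest on the assumed scores, noise and waning, with all eligible patients re-treated. Unscheduled visits could shift the starting week. Since the endpoints are tertiary and descriptive, this is a matter of how the tables can be read, and it is worth correcting because the correction is cheap.

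**What to change.** In SAP 4.1.3:

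1. Keep the by-week tables. Footnote MG-ADL and QMG rows from Week 11 on as conditional on not having been re-treated, and print beside them the number who started the cycle and the cumulative number re-treated.
2. For each cycle started in Part A, add a Kaplan-Meier summary, with numbers at risk, of time from first dose to loss of response. The event is the first of: meeting the protocol's MG-ADL re-treatment criteria, re-treatment, rescue therapy, or discontinuation for treatment failure or MG worsening.
3. Censor at end of Part A or at discontinuation for other reasons. Do not exclude all early discontinuations: rescue therapy and three consecutive treatment failures both lead to discontinuation (Protocol 4.1, 4.4), so exclusion would remove failures.
4. Do not use last-value-carried-forward.

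Restricting the summary to cycles started in Part A matches Protocol 3.3, which lists these endpoints for Part A only. Cycle 1 will be the cleanest curve. In later cycles the time left to end of Part A depends on how long earlier cycles lasted, so censoring may not be independent, and the table should say so.

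The cost is one extra table with its derivation, including the non-ocular share from the MG-ADL items, and no new data collection. The downside is that the later-week picture will look less favourable.
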